10.6 Subgroup Analyses

Efficacy endpoints (OS and PFS) will be assessed for the following subgroups on an as-stratified basis at randomization using the similar methodologies described in Section 10.2 and Section 10.3.

- Region of the world (North America (includes USA and Canada) and rest of the world (ROW))
- RPA classes (III, IV, and V)
- *MGMT* methylation (methylated and unmethylated)
- *EGFRvIII* status (mutated and other)

In addition, Forest plot for OS and PFS will be generated to display the HR with 95% CI for the subgroups defined by stratification factors, age categories (< 65, 65 - < 75,

≥ 75 years), gender (male and female), KPS categories (< 80, 80 - 90, 100), time from diagnostic GBM surgery to start of study treatment (< 4, 4 - 6, > 6 weeks), and type of surgery (gross total resection, partial resection, biopsy).

10.7 Pharmacokinetic Analyses

Analysis of pharmacokinetics of Depatux–M, total ABT-806, and free cys-mcMMAF are not covered in this SAP and will be described in a separate document.

11.0 Safety Analyses

11.1 General Considerations

Safety analysis will be carried out in the safety population. For most the safety endpoints (e.g., AEs, lab values, vital sign values and ECG values) except for TOE assessments, only the treatment emergent (TE) assessments (as defined in Section 7.3) will be included in the analyses. Incidence of TEAEs and treatment emergent lab abnormalities will be summarized in chemo-radiation phase and adjuvant phase separately and also in the overall study. A summary of continuous safety endpoints (e.g., change from baseline values in laboratory values, vital signs parameters) will include the mean, standard deviation, median and range. In the context of change from baseline analyses, summary of baseline and post-baseline data will also be provided. Categorical safety endpoints (e.g., incidence of AEs, incidence of potentially clinically significant values) will be summarized using frequencies and percentages. All the analyses will be carried out by treatment groups.

11.2 Analysis of Adverse Events

11.2.1 Treatment-Emergent Adverse Events (TEAEs)

TEAEs are defined as any AE with onset or increased severity after the first dose of study drug (RT/TMZ/Depatux–M or matching placebo) and no more than 49 days after the last dose of Depatux-M/placebo. Incidence of TEAEs will be summarized in chemo-radiation phase and adjuvant phase separately and also in the overall study.

Chemo-radiation phase is defined as from the Study Rx Day 1 to the day before the first adjuvant dosing. If adjuvant dosing is missing then, last Depatux-M/Placebo dosing + 49 days would be the end date of chemo-radiation phase. Adjuvant phase is defined as day of first adjuvant dosing to the last Depatux-M/Placebo dosing + 49 days.

Adverse Event Overview

The number and percentage of subjects experiencing TEAEs between the treatment groups will be summarized for the following adverse event categories.

- Any TEAE
- Any TEAE possibly related to any study drug
- Any TEAE possibly related to Depatux-M, TMZ and RT, separately
- Any TEAE with CTCAE grade 3 or higher
- Any TEAE with CTCAE grade 4 or higher
- Any Grade 3 or higher TEAE possibly related to any study drug
- Any Grade 3 or higher TEAE possibly related to Depatux-M, TMZ and RT, separately
- Any Grade 4 or higher TEAE possibly related to any study drug
- Any Grade 4 or higher TEAE possibly related to Depatux-M, TMZ and RT, separately
- Any TE serious AE (SAE)
- Any TE SAE possibly related to any study drug
- Any TE SAE possibly related to Depatux-M, TMZ and RT, separately
- Any TEAE leading to discontinuation of Depatux-M or Placebo, TMZ and RT, separately
- Any TEAE leading to discontinuation of Depatux-M possibly related to any study drug
- Any TEAE leading to discontinuation of Depatux-M/Placebo, possibly related to Depatux-M
- Any TEAE leading to discontinuation of TMZ, possibly related to TMZ
- Any TEAE leading to discontinuation of RT, possibly related to RT

- Any TEAE leading to dose-reduction of any study drug
- Any TEAE leading to dose-interruption of any study drug
- Any TEAE leading to death
- Deaths

This overview output will also be generated for each AESI, separately.

Adverse Events by System Organ Class and Preferred Term

The number and percentage of subjects experiencing TEAEs will be tabulated according to the primary MedDRA system organ class (SOC) and MedDRA preferred term (PT) for each treatment group. Subjects reporting more than one adverse event for a given MedDRA PT will be counted only once for that term. Subjects reporting more than one type of adverse event within a MedDRA SOC will be counted only once for that SOC. Subjects reporting more than one type of adverse event will be counted only once in the overall total.

AEs by Preferred Term

The number and percentage of subjects experiencing adverse events will be tabulated according to the MedDRA PT for each treatment group. Subjects reporting more than one AE for a given MedDRA PT will be counted only once for that term.

AEs by Maximum Severity

Adverse events will be summarized by SOC, PT and maximum severity per NCI CTCAE v.4 grading in each treatment arm. If a subject has an AE with unknown severity, then the subject will be counted in the severity category of "unknown," unless the subject does not have another occurrence of the same AE with a severity present. In addition, Grade 3 or higher AE and Grade 4 or higher events will also be summarized by SOC and PT.

AEs by Relationship

Adverse events possibly related to Depatux–M, TMZ, and radiotherapy as assessed by the investigator, will be summarized separately in each treatment arm. Following summaries

will be presented for the AEs possibly related to Depatux-M, TMZ, and radiotherapy, separately:

- Summary of AE by PT (possibly related to Depatux-M and TMZ only)
- Summary of AE by SOC and PT (possibly related to Depatux-M and TMZ only)
- Summary of Grade 3 or higher AE by SOC and PT
- Summary of Grade 4 or higher AE by SOC and PT
- Summary of SAE by SOC and PT
- Summary of Depatux-M/Placebo discontinuation by SOC and PT (possibly related to Depatux-M only)
- Summary of TMZ discontinuation by SOC and PT (possibly related to TMZ only)

If a subject has an AE with unknown relationship, then the subject will be counted in the relationship category of "unknown," unless the subject does not have another occurrence of the same AE with a relationship present.

AE of special interest (AESI)

AESIs will be assessed and summarized using standardised MedDRA query (SMQ) or AbbVie-defined company MedDRA query (CMQ). The AESIs below include events related to identified or potential risks of Depatux-M (corneal epitheliopathy, hepatotoxicity), events that are anticipated to occur in the study population due to underlying GBM or RT/TMZ treatment and independent of depatuxizumab mafodotin exposure (seizures, venous thromboembolic events, thrombocytopenia, neutropenia, infection), and events commonly associated with biologic therapies (hypersensitivity reactions). Specific AESI will be identified by the following search criteria:

AESI	Search Criteria ^a
Corneal Epitheliopathy (corneal AE)	CMQ "80000184"; Preferred Terms: Topography corneal abnormal, Corneal abrasion, Injury corneal, Persistent corneal epithelial defect, Abnormal sensation in eye, Acquired corneal dystrophy, Conjunctival irritation, Corneal cyst, Corneal decompensation, Corneal defect, Corneal degeneration, Corneal deposits, Corneal disorder, Corneal epithelial microcysts, Corneal epithelium defect, Corneal erosion, Corneal exfoliation, Corneal hypertrophy, Corneal infiltrates, Corneal irritation, Corneal lesion, Corneal neovascularisation, Corneal oedema, Corneal opacity, Corneal perforation, Corneal striae, Corneal thinning, Dry eye, Excessive eye blinking, Eye irritation, Eye opacity, Eye pain, Eye paraesthesia, Eye pruritus, Eye ulcer, Foreign body sensation in eyes, Glare, Keratic precipitates, Keratitis, Keratitis interstitial, Keratitis sclerosing, Keratopathy, Lacrimation decreased, Lacrimation disorder, Lacrimation increased, Limbal stem cell deficiency, Noninfective conjunctivitis, Ocular discomfort, Ocular hyperaemia, Ocular surface disease, Ocular toxicity, Photophobia, Punctate keratitis, Scleral oedema, Scleral thinning, Superior corneal epithelial arcuate lesion, Superior limbic keratoconjunctivitis, Ulcerative keratitis, Vision blurred, Visual acuity reduced, Visual brightness, Visual impairment, Xerophthalmia, Cornea verticillata,
Hepatotoxicity	Drug related hepatic disorders - comprehensive search (Broad SMQ) – 20000006
Hepatotoxicity – severe events	Drug related hepatic disorders – severe events only (Broad SMQ) – 20000007
Thrombocytopenia	Haematopoietic thrombocytopenia Broad SMQ (SMQ, 20000031)
Neutropenia	Haematopoietic leukopenia Broad SMQ (SMQ 20000030)
Venous thromboembolic events	Embolic and thrombotic events, venous - Narrow SMQ (SMQ 20000084)
Infection events with 14 days after neutropenia events*	Infections - CMQ (CMQ 80000018) Hematological toxicity - neutropenia – Narrow CMQ (CMQ 80000154)
Hypersensitivity reactions	Hypersensitivity - Broad SMQ (SMQ 20000214)
Seizures	Convulsions - Narrow SMQ (SMQ – 20000079)

* Includes only infections that start anytime from start of neutropenia to end of neutropenia + 14 days.

a. Preferred terms are included in each CMQ are documented in ABT-414 Integrated Summary Safety (ISS) Statistical Analysis Plan.

Time to the first occurrence (onset) of any corneal AEs will be assessed using Kaplan Meier methodology and median time to first onset of any corneal AE (along with 95% CI). This analysis will be repeated for Grade 2 or higher corneal AEs, Grade 3 or higher corneal AEs, and Grade 4 or higher corneal AEs.

Time to onset will be measured in days relative to the date of first dose date to the start date of the first occurrence of corneal AE. If a subject has not experienced a corneal AE, the subject will be censored on the subject's last assessment date (i.e., the day of the subject's last known laboratory assessment, last known vital sign assessment, last known physical exam, last known ocular exam, last known tumor assessment, or last known follow-up visit, whichever is the latest) or 49 days from the subject's last treatment (Depatux–M or placebo), whichever is earliest. If the subject has not experienced a corneal AE and had no post-baseline assessment, the data will be censored on the day of first dosing date.

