7.3 Adverse Event Severity

The Investigator will rate the severity of each adverse event according to the National Cancer Institute Common Terminology Criteria for Adverse Events (NCI CTCAE Version 4.0)²⁷

For adverse events not captured by the Common Terminology Criteria, the following should be used:

Grade 1	The adverse event is transient and easily tolerated by the subject (mild).
Grade 2	The adverse event causes the subject discomfort and interrupts the subject's usual activities (moderate).
Grade 3	The adverse event causes considerable interference with the subject's usual activities and may be incapacitating (severe).
Grade 4	Life threatening; urgent intervention.
Grade 5	The adverse event resulted in death of the subject (severe).

Relationship to Protocol Treatment

The Investigator will use the following definitions to assess the relationship of the adverse event to the use of protocol treatment, with separate assessments for each component of therapy (ABT-414/placebo, TMZ and radiation therapy):

Reasonable Possibility	After consideration of factors including timing of the event, biologic plausibility, clinical judgment, and potential alternative causes, there is sufficient evidence (information) to suggest a causal relationship.
No Reasonable Possibility	After consideration of factors including timing of the event, biologic plausibility, clinical judgment, and potential alternative causes, there is insufficient evidence (information) to suggest a causal relationship.

Reasonable possibility is defined such that the specific treatment (ABT-414/placebo, TMZ, or radiation therapy) is more likely to be the cause of the event than any other reason, whereas no reasonable possibility is defined as the Other cause of the event is more likely. For causality assessments, events assessed as having a reasonable possibility of being related to protocol treatment will be considered "associated." Events assessed as having no reasonable possibility of being related to protocol treatment will be considered "not associated." In addition, when the Investigator has not reported a causality or deemed it not assessable, AbbVie will consider the event associated.

If an Investigator's opinion of no reasonable possibility of being related to protocol treatment is given, an Other cause of event must be provided by the Investigator for the serious adverse event.

[figure not shown]

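### The SAP's rule for adverse events with a missing grade has its condition reversed, which misclassifies subjects in the maximum-severity table; the parallel relationship rule also departs from Protocol Section 7.3.

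*SAP*

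**What the plan says.** SAP Section 11.2.1, under AEs by Maximum Severity, sets the purpose of the table: "Adverse events will be summarized by SOC, PT and maximum severity per NCI CTCAE v.4 grading in each treatment arm". It then deals with missing grades. By default, a subject with an ungraded event goes into a category named *unknown*. The exception to that default is worded as follows: "unless the subject does not have another occurrence of the same AE with a severity present".

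Under AEs by Relationship the same construction returns. The default again sends a subject whose event lacks a relationship to *unknown*, and the exception is worded in the same way: "unless the subject does not have another occurrence of the same AE with a relationship present".

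Two other provisions bear on the rule. Under AEs by Preferred Term, the SAP fixes the counting unit: "Subjects reporting more than one AE for a given MedDRA PT will be counted only once for that term". Protocol Section 7.3 has its own convention for missing causality: "when the Investigator has not reported a causality or deemed it not assessable, AbbVie will consider the event associated". No other section of either document states the missing-grade rule the other way round or corrects it.

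**The concern.** A maximum-severity table needs one grade per subject and term. If any record of the term carries a grade, the highest one should stand. The unknown category is for subjects who have no grade at all. The sentence as written does the opposite for both groups.

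Repeat records of one term are to be expected, because Protocol Section 7.2.1.1 asks for a worsening of a reported event to be entered as a new event. That is the data structure in which one blank field could hide a recorded grade. Severity is also central to this drug's safety profile: the interim summary in Protocol Section 1.0 gives Grade 3 or higher events in 87.3% of subjects on ABT-414 and 62.3% on placebo. SAP Section 4.0 says that the document's conventions are there to guide programming, so a programmer must either apply the wrong rule or depart from the signed plan without a record of having done so.

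**Working it through.** No power, alpha or sample-size figure is involved. The check is a comparison of cases.

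**Severity.** The rule applies only to a subject with at least one ungraded record of the event. Two cases follow.

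| Records of the same event | SAP as written | Maximum-severity rule |
|---|---|---|
| Ungraded and graded | Exception not met: unknown | Highest recorded grade |
| Ungraded only | Exception met: exempt from unknown, no category named | Unknown |
| No ungraded record | Rule not triggered | Rule not triggered |

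The two versions disagree in both cases where the rule applies. Example: a subject with keratitis recorded once at Grade 3 and once without a grade is tabulated as unknown instead of Grade 3. A subject whose only keratitis record is ungraded has no severity category.

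**Relationship.** Here three conventions have to be compared: the SAP as written, the SAP with only the negative removed, and Protocol Section 7.3.

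| Records of the same event | SAP as written | Negative removed | Protocol 7.3 |
|---|---|---|---|
| Missing and related | Unknown | Related | Related |
| Missing and not related | Unknown | Not related | Related |
| Missing only | No category named | Unknown | Related |

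Removing the negative agrees with the protocol in only one of the three rows. It also gives no selection rule for a subject whose recorded relationships differ, since a highest grade has no counterpart there.

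**Which outputs are exposed.** The severity sentence governs the maximum-severity table. Other outputs are specified separately:
- the Section 11.2.1 overview counts subjects with any event of Grade 3 or higher, any of Grade 4 or higher, and any event possibly related to a treatment;
- the Grade 3 or higher and Grade 4 or higher tables by SOC and PT are introduced as additional summaries;
- serious events, deaths and Grade 3 or higher listings come under Sections 11.2.2 and 11.2.3.

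The outputs listed under AEs by Relationship are all restricted to events possibly related to a given treatment. None has a row for unknown relationship.

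**The case against.** The strongest defence is that this is a drafting slip whose intent is plain from the heading. The literal rule cannot even be fully programmed, because it leaves one group without a category, so a competent programmer would raise a query. Missing values should also be uncommon: Protocol Sections 7.2 and 7.3 require the investigator to record severity and relationship. All of this is fair. It keeps the point minor, but it does not make the sentence right, and the same reversal appears twice.

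A reader might infer more: that severe-event counts are understated, that related-event counts are understated, or that subjects with only missing grades vanish from the tables. The documents support none of these.
- One recorded Grade 3 event qualifies a subject for the any-event overview line whatever another record lacks. Nothing in the SAP says that the Grade 3 or higher and Grade 4 or higher summaries are built from the maximum-severity category.
- A subject with one recorded related event likewise meets the possibly-related overview criterion, and no listed output carries an unknown-relationship row into which that subject would be moved.
- Subjects with only ungraded records still count under their SOC and PT. What they lack is a severity category.

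On relationship, one could answer that the SAP tables use the investigator's assessment while Section 7.3 describes how the sponsor treats a missing one. That may explain the mismatch, but the SAP does not say that it is departing from the protocol convention, so the two still need reconciling.

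**Conclusion.** The severity rule in SAP Section 11.2.1 is wrong as written. In the maximum-severity table it gives the wrong category to a subject with both graded and ungraded records of an event, and no category to a subject with only ungraded records. For subjects to whom the rule applies, the error occurs every time. How many there are is not given, so no overall size can be stated, and it may be zero. The Grade 3 or higher and Grade 4 or higher summaries are affected only on the assumption, not stated in the SAP, that they are derived from the same per-subject category. The relationship sentence has the same reversal and in addition does not match Protocol Section 7.3. No efficacy result, error rate or power figure is involved. This is a minor but clear wording correction.

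**What to change.** In the severity sentence, change *does not have* to *has*, and add that the highest recorded grade for that event is then used. Subjects with only ungraded records then fall in the unknown category.

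Replace the relationship sentence with a rule that follows Protocol Section 7.3: for each treatment component, a subject with any occurrence of the event that is related, or whose causality is unreported or not assessable, is counted as related.

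It would help to add that the Grade 3 or higher and Grade 4 or higher summaries are taken from all graded records and not from the maximum-severity category. If the tables have already been programmed, record which rule the code applied.

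The cost is two revised sentences, one optional clarification and a check of the table code. No new data are needed.

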6.0 Analysis Populations

The database for Study M13-813 includes subjects for the main part of the study as well as patients in the China sub-study (which enrolls Chinese patients) and hepatic impairment sub-study. The main part of the study targeted enrollment of 640 randomized subjects (i.e., not including open-label hepatic sub-study subjects). The enrollment of the main part of the study was closed on 31-Mar-2018, and all subjects randomized by that date were to be included in the main study analysis population. Enrollment for the Chinese sub-study cohort remains ongoing, and Chinese subjects enrolled after 31-Mar-2018 will not be included in the main study analysis population. Patients enrolled in the open-label hepatic impairment sub-study will not be included in the main study analysis population.

A total of 639 subjects, including 2 subjects in the Chinese cohort, were enrolled by 19-Mar-2018 and will be included in the main study analysis population.

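### SAP 11.2.1 classes adverse events of unknown causality as 'unknown', while Protocol 7.3 counts them as associated, so related counts may be lower wherever causality is missing

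*SAP*

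**What the plan says.** Protocol 7.3 (Relationship to Protocol Treatment) has the investigator assess each adverse event separately against ABT-414/placebo, TMZ and radiation. It has two classes, associated and not associated: "events assessed as having a reasonable possibility of being related to protocol treatment will be considered" associated. It then fills the gap left by absent assessments: "when the Investigator has not reported a causality or deemed it not assessable, AbbVie will consider the event associated". The sentence is not limited to serious events or to expedited reports.

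SAP 11.2.1 (AEs by Relationship) says that events possibly related to Depatux-M, TMZ and radiotherapy, "as assessed by the investigator, will be summarized separately in each treatment arm". Seven summaries follow. After them comes the rule for absent assessments: "If a subject has an AE with unknown relationship, then the subject will be counted in the relationship category of", where the category named is unknown. An exception is attached to this rule: "unless the subject does not have another occurrence of the same AE with a relationship present".

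The Adverse Event Overview, earlier in SAP 11.2.1, uses relatedness in lines such as "Any TEAE possibly related to any study drug" and "Any TEAE possibly related to Depatux-M, TMZ and RT, separately". It gives no rule for missing causality. The overview is also to be repeated for each adverse event of special interest.

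**The concern.** The same record is associated under the protocol and outside the related class under the SAP. The SAP presents itself as the detailed methods for the study as outlined in the protocol, yet it does not mention the default, and its summary of changes does not record a departure from it.

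The choice also runs against the SAP's own practice for other missing safety data. An event with an incomplete onset date is assumed treatment-emergent (SAP 7.3), and prior and concomitant medications are classified by an approach that the SAP calls conservative (SAP 8.3).

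Comparative safety is a stated objective. At stake is whether the related-event counts agree with the protocol rule and with each other. Because the overview is silent, a programmer could apply the protocol default there and the unknown category in the by-relationship tables. One report would then hold two related counts for the same data.

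**Working it through.** The documents state no figure on this point, so there is none to reproduce. The check is a comparison of the rules, followed by an illustration of scale.

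**Rules side by side.** Take one subject, one adverse event term and one treatment component. 'Repaired' means that the exception is read as applying when another assessed occurrence does exist, which is presumably what was meant.

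| Subject's records for the event | Protocol 7.3 | SAP, literal | SAP, repaired |
|---|---|---|---|
| Unknown only | Associated | Exempt from unknown; no category given | Unknown |
| Unknown and related | Associated | Unknown | Related |
| Unknown and not related | Associated | Unknown | Presumably not related |
| All assessed | As assessed | As assessed | As assessed |

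Repairing the exception restores agreement in the second row only. The first and third rows still differ from the protocol. In both, the subject has an unassessed record and nothing assessed as related. The difference runs one way: a count that leaves out unknowns is at or below the count under the protocol rule.

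**Where the SAP rule applies.** It is written for the seven by-relationship summaries. The any-grade summaries there cover Depatux-M and TMZ only, and the discontinuation summaries cover Depatux-M/placebo (one) and TMZ (one). No any-grade or discontinuation table for radiotherapy is listed. Those radiotherapy lines appear only in the overview, where 12 lines use 'possibly related' and no rule is given.

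**Scale per subject.** SAP 6.0: "A total of 639 subjects, including 2 subjects in the Chinese cohort, were enrolled by 19-Mar-2018". With 1:1 randomisation, 639/2 = 319.5, or about 320 per arm. The safety set may be slightly smaller.
- One affected subject: 1/320 = 0.31 points.
- Three affected subjects: 3/320 = 0.94 points.

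**Illustration, all three inputs assumed.** Let p be the share of event records with missing causality, q the share related among assessed records, and k the number of independent records per subject in a row.
- Protocol rule: 1 − [(1 − p)(1 − q)]^k
- Unknowns left out (repaired reading): 1 − [1 − (1 − p)q]^k

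Example with p = 1%, q = 0.3, k = 3: protocol 1 − 0.693³ = 66.72%; unknowns left out 1 − 0.703³ = 65.26%; gap 1.46 points.

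| p | q | k | Gap (points) | Subjects of 320 |
|---|---|---|---|---|
| 0 | any | any | 0 | 0 |
| 1% | 0.3 | 1 | 1.00 | 3.2 |
| 1% | 0.3 | 3 | 1.46 | 4.7 |
| 1% | 0.3 | 10 | 0.39 | 1.3 |
| 5% | 0.6 | 10 | 0.02 | 0.0 |
| 5% | 0.1 | 10 | 15.98 | 51.1 |

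With p from 0% to 5%, the gap runs from 0 to about 16 points. That range is too wide to serve as an estimate. It shows that the effect depends on quantities the documents do not give.

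**The case against.** The strongest reply is that the two rules answer different questions. The SAP tables are labelled investigator-assessed, and the protocol default is a sponsor classification. A table of investigator assessments with blanks shown as unknown is a legitimate display. The protocol's own safety-analysis text has no causality imputation rule. If the sponsor default is applied to the data before tabulation, the unknown category would be empty. Part of this stands: neither document says at which stage the default is applied. It does not remove the conflict. The default operates only where the investigator gave no usable assessment, so it overrides nobody, and neither document says that the two rules serve separate purposes.

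A second reply is that little causality will be missing. Protocol 7.2 requires the relationship to be recorded for each event, Protocol 11.2 provides for review of case report forms for completeness, and a serious event judged unrelated must carry another cause. This is fair, and it is why a zero effect is a real possibility.

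A third reply is that the main safety comparison does not rest on these tables. This also stands. The all-causality summaries (any event, Grade 3 or higher, Grade 4 or higher, serious, leading to discontinuation) are untouched. Serious, fatal, Grade 3 or higher and discontinuation events are listed individually. Events of special interest are identified by MedDRA queries, not by causality. The rule is the same in both arms.

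**Conclusion.** The conflict holds: for missing or not-assessable causality, SAP 11.2.1 states a rule that differs from Protocol 7.3 and gives no reason. Where such a record belongs to a subject with no event assessed as related in that row, the possibly-related count is lower than under the protocol rule, by about 0.31 points per subject in an arm of about 320. This assumes the repaired reading of the exception. The literal reading is worse: it leaves the unknown-only subject without a category, and it sends a subject with a related occurrence to unknown.

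A reader might infer that every possibly-related table undercounts. The documents do not support that. They give no rate of missing causality. A row is unaffected if all its unassessed records belong to subjects already counted as related. For the overview the SAP is silent, not contradictory. Nor do they support a claim about any-grade or discontinuation tables for radiotherapy among the by-relationship summaries, since none is listed.

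A reader might also infer that rare, serious related events would lose half their count. In an arm of 320, an event in 1–2% of subjects is about 3 to 6 subjects, so three affected subjects would matter that much. Nothing in the documents indicates that three, or any, would be affected.

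No efficacy conclusion is touched. The point is worth correcting because it is a direct inconsistency that is cheap to remove.

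**What to change.** Replace the unknown-relationship sentence in SAP 11.2.1 with: 'AEs with missing or not-assessable causality are counted as related to that component (Depatux-M/placebo, TMZ, RT) in the overview and by-relationship summaries, per Protocol 7.3.' List these events, or report their number per arm and component, so that a reader can see how much of each related count comes from the default.

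This removes the inverted exception for relationship and gives the overview a rule. The sentence on unknown severity, under AEs by Maximum Severity, has the same inverted exception and should be corrected in the same edit.

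If the sponsor prefers to keep an unknown category, the SAP should say so, justify the departure from Protocol 7.3, correct the exception, and state the rule for the overview as well.

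The cost is one sentence, one derivation and one listing or count. The downside is that related rates become equal or slightly higher, and include some events that no investigator judged to be related. The reported number of defaulted events makes that visible.
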